4.9. Justification for Dose Levels and Dose Intervals

The proposed dose levels of 25, 100, and 200 mg are each expected to produce PD effect. In the AROAAT1001 study, doses of 35, 100, and 200 mg yielded substantial serum AAT reductions, with both 100 and 200 mg reaching approximately 90% mean serum AAT reduction after multiple doses in the AROAAT1001 study. All proposed doses are below the top dose of 300 mg, which was studied as both single and multiple (3) doses in AROAAT1001. In the Phase 1 study, dose levels up to the top dose of 300 mg were well tolerated with no serious or severe AEs reported in the study to date and no pattern of adverse laboratory changes associated with fazirsiran. All 3 proposed dose levels are expected to provide varied and dose dependent PD effect and are well within a margin of safety based on previous human testing as well as rat and NHP GLP toxicity studies. A bracketing dose design was chosen based on doses and serum AAT activity observed in AROAAT1001 using the lowest dose expected to generate maximal intrahepatic reduction (100 mg) bracketed by one lower dose level (25 mg) and one higher dose level (200 mg). Serum AAT reductions with single and multiple doses of fazirsiran at the 100 and 200 mg dose levels were similar in the AROAAT1001 study with both appearing to generate maximal serum reductions. Single 35 mg doses appear to be less active than 100 mg with regards to serum AAT reduction. It is presently unknown whether AATD patients will exhibit a similar sensitivity to ARO-AAT Injection, i.e., whether near full reduction in serum AAT in healthy volunteers correlates to patient liver reductions. However, data from other siRNA compounds

targeting AAT indicate that PiZZ patients respond to hepatocyte targeted siRNA silencing of AAT in a manner similar to healthy volunteers at equivalent dose levels (Turner et al., 2018). Finally, although similar serum AAT reduction, following multiple doses of 100 and 200 mg, were observed, there is less inter-subject variability in serum AAT reduction at the higher dose level and an apparent longer duration of effect. It is possible that 200 mg will produce greater suppression in liver Z-AAT production than the 100 mg dose. Arrowhead believes the greater the suppression of liver Z-AAT protein production, the greater potential for improvement in disease. This is based on other liver diseases such as HBV/HCV, where full or near full removal of the insulting agent has been observed to allow the liver to begin the regenerative process.

The rationale for the proposed dosing interval is based on the goal of targeting AATD patients exhibiting liver fibrosis with the aim of halting the liver insult and damage produced by polymerized aggregates of Z-AAT as early and effectively as possible. Providing a dose on Day 1 followed by a dose on Day 29 (Week 4) is likely to more rapidly drive hepatic AAT levels to maximally reduced levels (similar to a loading dose strategy) followed by a maintenance dose 12 weeks after the second dose on Day 113 (Week 16) and dosing approximately quarterly thereafter. This strategy of maximizing ablation of liver AAT early should yield the most benefit to patients in terms of liver PiZ protein reduction over the course of the study, while then moving to quarterly dosing should maximize safety by limiting patient exposure to drug. The administration of the third fazirsiran dose (and subsequent doses later in development) at Day 113 (Week 16) and quarterly dosing thereafter is based on AROAAT1001 single dose data showing duration of PD activity with rebound in serum AAT levels beginning approximately 12 weeks after dose administration. Approximate quarterly dosing should minimize additional unnecessary dosing and minimize safety risk.

In chronic GLP toxicity studies in rats and monkeys, adverse findings were not identified, with the NOAELs of 120 mg/kg in rats and 180 mg/kg in monkeys, which in both cases were the highest doses tested. The planned doses used in this study of 25, 100, and 200 mg are approximately 1/336th, 1/84th, and 1/42nd, respectively, (assuming weight-based conversion and a 70-kg subject) of the rat NOAEL of 120 mg/kg and 1/504th, 1/126th, and 1/63rd, respectively, of the 180 mg/kg monkey NOAEL from chronic GLP toxicity studies. Additionally, the doses used in this study are lower than the 300 mg dose level which was administered for 3 Q28 doses in the AROAAT1001 study and was well tolerated.

5. OBJECTIVES

5.1. Primary Objective

To select a single dose for use in later stage development based on a combined evaluation of safety and PD effects of fazirsiran

5.2. Primary Endpoint

• Percent change from baseline at Week 16 in serum Z-AAT

5.3. Secondary Endpoints

- Subject incidence of treatment-emergent AEs
- Absolute and percent change from baseline in total liver Z-AAT (insoluble + soluble) protein at post-dose biopsy visit
- Absolute and percent change from baseline in liver Z-AAT soluble protein at post-dose biopsy visit
- Absolute and percent change from baseline in liver Z-AAT insoluble protein at post-dose biopsy visit
- Absolute and percent change from baseline in liver function tests including ALT, aspartate aminotransferase (AST), alkaline phosphatase (ALP), gamma glutamyl transferase (GGT), total bilirubin, direct bilirubin, and international normalized ratio (INR) at Week 16 and over time through End of Study (EOS)
- Absolute and percent change in serum Z-AAT over time through EOS
- Change over time in PK measurements of fazirsiran at timepoints specified in the Schedule of Assessments (SOA)
- Incidence of anti-drug antibodies (ADAs) to fazirsiran
- Change from baseline in Metavir fibrosis stage at post-dose biopsy

5.4. Exploratory Endpoints

- Change from baseline in liver histology (e.g., globules, inflammation, steatosis) at post-dose biopsy
- Change from baseline in hepatic SERPINA1 mRNA expression at post-dose biopsy
- Change from baseline in liver fibrosis gene expression at post-dose biopsy

- Absolute and percent change from baseline in serum PRO-C3 at Week 16 and over time through EOS
- Change from baseline in noninvasive scoring systems for fibrosis, including aspartate aminotransferase-to-platelet ratio index (APRI) and FIB-4, at Week 16 and over time through EOS
- Change from baseline in FibroScan® over time through EOS
- Change from baseline in hepatic stiffness based on magnetic resonance elastography (MRE) (if available) over time and through EOS
- Change from baseline in hepatic fat content based on MRI (MRI) (MRI-proton density fat fraction [MRI-PDFF] if available) over time and through EOS
- Change from baseline in hepatic iron content based on MRI (if available) over time and through EOS
- Change from baseline in markers of liver fibrosis, globules, and iron content using biomarkers (e.g., PRO-C6) and special stains and imaging (Masson's Trichrome, Sirius Red, Iron, PAS-D), which may include histologic morphometric analysis (if scientifically feasible and sufficient sample available), over time and through EOS

6. STUDY PLAN

6.1. Study Design

A multi-center, multi-dose placebo-controlled Phase 2 study will be conducted to evaluate the safety, efficacy, and tolerability of the investigational product, fazirsiran, administered subcutaneously to patients with AATD.

Study Details

The study will test 3 dose levels compared to placebo. Patients who have signed an Institutional Review Board (IRB)/Ethics Committee (EC) approved informed consent and have met all the protocol eligibility criteria during Screening will be assigned to one of 3 cohorts and randomized 2:1 (active: placebo) within each cohort. The 3 cohorts of the study are as follows:

- Cohort 1: 25 mg dose of fazirsiran or placebo
- Cohort 2: 100 mg dose of fazirsiran or placebo
- Cohort 3: 200 mg dose of fazirsiran or placebo

Within each cohort, requirements for biopsies, dosing schedules, and SOA will be determined based on the patient's fibrosis score during Screening.

Patients With No Evidence of Fibrosis

Patients who have a documented biopsy showing no evidence of fibrosis within 1 year of the Screening visit will not require liver biopsy at any point during the study.

Patients without fibrosis at Screening will receive 2 doses of fazirsiran or placebo on Day 1 and Week 4, as per the SOA. Following their Week 4 dose, these patients remain in the study with regular visits per the SOA until Week 64.

Patients With Evidence of Fibrosis

Patients who have a pre-dose biopsy showing evidence of fibrosis (without definitive cirrhosis) during Screening will have a post-dose biopsy performed at Week 48. If a patient is beyond Week 48 at the time of IRB/EC approval of Protocol v4.0, then the post-dose biopsy will occur at Week 72 or 96. The study will end after the last patient with fibrosis receives their 10th dose (Week 100 visit) or until a long-term extension study is available at the subject's study site, whichever comes first.

[figure not shown]
Patients with evidence of fibrosis at Screening will receive a dose on Day 1, Week 4, and Week 16, then every 12 weeks for up to 18 doses total. A Study Completion visit will occur between 4 to 12 weeks after a patient's last study treatment dose.

Dose Evaluation and Selection

After all enrolled patients completed the Week 16 visit, an Interim Analysis was performed to select a single dose level (25, 100, or 200 mg) for the open-label phase of the study. Based on cumulative safety, efficacy, and PD data from the fazirsiran clinical program (clinical studies AROAAT1001, AROAAT2001, and AROAAT2002), a fazirsiran dose (200 mg) was selected

by the Sponsor. All patients with fibrosis at Screening who completed the post-dose biopsy visit at Week 48 (or Week 72 or 96) will receive fazirsiran at the selected dose for the duration of the study (open-label phase) but will remain blinded to their randomized treatment assignment.

Figure 1: Study Schema

6.2. Rationale for Study Design

The study is intended select a dose to be used in later stage development clinical studies and to collect noninvasive markers of liver disease alongside liver biopsy data to demonstrate the relationship of reduction of intrahepatic Z-AAT protein levels to improvement in biomarkers of liver disease. Tissue samples from percutaneous liver biopsy will be required. Other markers of liver injury such as fibrosis score will also be measured on biopsy. Biopsy will be conducted predose and post-dose for patients with evidence of fibrosis at Screening. The study will enroll PiZZ patients without definitive cirrhosis. Patients without evidence of fibrosis will be able to participate in a limited portion of the study. The study uses a placebo arm to help evaluate the safety of fazirsiran in an AATD patient population. The study is double-blind to limit the occurrence of conscious and unconscious bias in trial conduct and interpretation. Blinding will be achieved using a placebo (PBO) (0.9% normal saline) volume matched injection. Inclusion of patients receiving PBO will reduce bias in the assessment of drug safety and tolerability.

In the study, 3 separate dose levels are used to test if there is a dose-response in safety and PD assessments. After all enrolled patients completed the Week 16 visit, an Interim Analysis was performed to facilitate the dose selection. As changes in serum Z-AAT levels in response to fazirsiran is the primary objective of the study, any patient who does not have cirrhosis is eligible to participate. Dose and PD response in patients with cirrhosis will be studied in a separate trial designed for a hepatic impairment population.

Non-cirrhotic PiZZ AATD patients are an appropriate population to conduct dose-finding as serum Z-AAT is readily measured and levels are uninfluenced by fibrosis stage. Thus, all PiZZ patients (without definitive cirrhosis) can participate. Patients without evidence of fibrosis will only receive 2 doses and will not have a post-dose biopsy or continue into the open-label phase as they have no evidence of fibrosis and would be likely to have minimal to no histological

changes following treatment. Therefore, patients with a documented biopsy result showing no evidence of fibrosis within 1 year of screen, will not require a baseline biopsy. In order to maximize the available efficacy data and ensure sufficient samples for analysis of liver biopsies, a minimum of 24 patients with evidence of fibrosis will be enrolled.

Fibrosis patients will have a screening liver biopsy and a second biopsy at Week 48. Changes in liver Z-AAT, adverse liver histological findings and liver injury biomarkers due to AATD liver disease are expected to require 6 months or longer of therapy to show improvement. Thus, a post-dose liver biopsy in patients with evidence of fibrosis at Screening will be taken at Week 48 (if a patient is beyond Week 48 at the time of IRB/EC approval of Protocol v4.0, then the post-dose biopsy will occur at Week 72 or 96).

The open-label phase of the study is intended to collect long-term safety of fazirsiran.

6.3. DSMB and Stopping Rules

An independent DSMB consisting of 2 hepatologists and a pulmonologist and aided by an unblinded biostatistician will review the unblinded data generated from this study after the first 18 patients have received at least one dose of study drug and completed the Week 16 visit, or as needed in emergent safety related circumstances. An independent statistical center (ISC) will provide unblinded comparative safety summaries to the DSMB in a restricted manner. The Sponsor will not have access to the unblinded summaries. This planned safety review will include evaluations for imbalances between active and placebo groups for pulmonary AEs as well as clinically significant adverse changes in FEV₁ and DLCO. The DSMB may be asked to review safety data at additional unscheduled meetings should a potential safety signal be detected. The DSMB will also be involved in decisions to evaluate individual patients for discontinuation (See study modification rules in Appendix 2 and Appendix 3). The DSMB may also make recommendations regarding modification of individual study cohorts and/or study design.

A decision to stop the trial early or discontinue drug in an individual patient or group of patients may be indicated based on any of the following:

- 1. In the case of 2 or more similar serious adverse events (SAEs) both considered at least possibly related to fazirsiran, the DSMB will meet within 3 days of the DSMB being notified of the second event and within the timeframe of required regulatory agency notification. The DSMB will review available aggregated data to determine if the study remains safe to proceed, should be discontinued, or should continue but with amendments.
- Evaluation and fazirsiran study modification/discontinuation rules for elevated liver tests signaling worsening AATD liver disease or drug induced liver injury (DILI) are provided in Appendix 2.
- 3. Evaluation and fazirsiran study modification/discontinuation rules for declines in pulmonary function are provided in Appendix 3.

Any discontinued patient will be followed with appropriate assessments and monitoring (either per SOA or with more intensive evaluation) through EOS. Sponsor or Investigator can discontinue any patient at any time with or without DSMB consultation. If such events (as described in #1 through #3 above) occur and the patient is not discontinued from the study, the reason for not discontinuing the patient will be included in DSMB meeting minutes. Including, but not limited to the events listed above, the DSMB may pause the study to additional dosing to provide time to evaluate safety data and recommend the action to be taken, which may include, but is not limited to, one of the following:

- Discontinuation of a patient or group of patients from the study
- The study is stopped immediately with no further dosing
- The study will continue, but using a lower dose
- The study will continue as planned

Arrowhead will notify the concerned regulatory agencies and ethics committees immediately and at least within 15 days from when the trial is temporarily halted or prematurely discontinued. A substantial protocol amendment will be submitted to the concerned regulatory agencies clearly explaining the reasons and scope, e.g., stopping recruitment and/or interrupting treatment of all patients already included. Furthermore, to restart the trial, the request will be submitted in form of a substantial amendment providing evidence that it is safe to restart the trial. If Arrowhead decides not to recommence a temporarily halted trial, the concerned regulatory agency(-ies) will be notified within 15 days of this decision, providing a brief explanation of the reasons for ending the trial.

6.4. Duration of the Study

The duration of the study is as follows:

Patients without fibrosis: up to 72 weeks, as follows:

Screening: up to 8 weeks

Dosing and Follow-up: up to 64 weeks. Study treatment will be administered on Day 1 and Week 4.

Patients with evidence of fibrosis: up to 216 weeks, as follows:

Screening: up to 8 weeks

Dosing through end of open-label phase: up to 196 weeks, followed by a Study Completion visit 4 to 12 weeks after the last dose in the open-label phase. Up to 18 doses of study treatment will be administered (Day 1, Week 4, Week 16 followed by a dose once every 12 weeks up to Week 196).

7. PATIENT SELECTION

7.1. Number of Patients and Patient Demographics

This study will be conducted in PiZZ patients with confirmed alpha-1 antitrypsin deficiency. Both males and females are eligible, ages 18 to 75 years. In total, the study will consist of approximately 36 patients. A minimum of 24 out of 36 patients must have evidence of fibrosis on the liver biopsy at Screening. All eligible patients will require a pre-dose biopsy completed as part of the study.

7.2. Inclusion Criteria

To be eligible for enrollment, patients must meet all the following inclusion criteria:

- 1. Male or non-nursing female patients 18 to 75 years of age, inclusive, at the time of Screening with previous diagnosis of PiZZ genotype alpha-1 antitrypsin deficiency. PiZZ diagnosis from source verifiable medical records is permitted. Otherwise, patients must undergo PiZZ confirmatory testing at Screening. PiMZ or PiSZ genotypes are not permitted.
- 2. Able and willing to provide written informed consent prior to the performance of any study specific procedures.
- 3. Liver biopsy indicating a liver fibrosis score less than F4 based on local pathologist read.
 - a. A patient with no fibrosis may participate based in a previous biopsy conducted within one year if a source verifiable medical record specifies no evidence of fibrosis.
- 4. A 12-lead electrocardiogram (ECG) at Screening that, in the opinion of the Investigator, has no new acute abnormalities (e.g., new onset atrial fibrillation) that compromise patient's safety in this study. Stable disease (e.g., stable atrial fibrillation) is acceptable.
- 5. Non-smoker (defined as does not smoke cigarettes daily for at least 12 months) with current non-smoking status confirmed by urine cotinine at Screening and throughout the study AND any previous smoking history prior to 12 months must be <15 pack years. Patients may be on nicotine replacement (patch or gum). E-cigarettes (vapor) are not permitted. A positive urine cotinine result due to nicotine replacement is acceptable for enrollment at the discretion of the Investigator.
- 6. Use highly effective contraception during the study and for 3 months following the last dose of fazirsiran. Males must not donate sperm for at least 3 months post last dose of study treatment. Women of childbearing potential (WOCBP) must have a negative urine pregnancy test at Screening and on Day 1 pre-dose. Women not of childbearing potential must be post-menopausal (defined as cessation of regular menstrual periods for at least 12 months without an alternative medical cause), confirmed by follicle-stimulating hormone (FSH) consistent with post-menopausal state based on lab reference ranges.

- Using twice the normal protection of birth control by using a condom AND one other form of either birth control pills (The Pill), depot or injectable birth control, intrauterine device (IUD), birth control patch (e.g., Ortho Evra), NuvaRing®, OR Surgical sterilization as a single form of birth control: i.e., tubal ligation, hysterectomy, bilateral oophorectomy, vasectomy, or equivalently effective surgical form of birth control, is acceptable.
- True abstinence for the duration of the study and 12 weeks after the dose of fazirsiran is acceptable only when in line with the preferred and usual lifestyle of the patient. Periodic abstinence (calendar, symptothermal, post-ovulation methods), withdrawal (coitus interruptus), spermicides only, and lactational amenorrhea methods are not considered "true" abstinence and are not acceptable methods of contraception.
- * All laboratory tests used as inclusion criteria may be repeated once and the repeat value may be used for inclusion purposes.

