- Negative urine pregnancy test must be confirmed pre-dose on dosing days in pre-menopausal females.

Table 2: Schedule of Assessments – Patients With Evidence of Fibrosis

Assessment	Scree	en	Day 1 (Dosing	24 hrs After	Week 2	Week 4	24 hrs After	Week 6	Week 16	24 hrs After	Continue	Additional Dosing Visits Every	24 hrs After	Post-Dose Liver Biopsy ⁵	90 Days Post Last	Study Com-	Early Term- ination ⁸
	Requi Prior Day	r to	Day)	Dosing Day 1	Day 15	Day 29 (Dosing Day)	Dosing Day 29	Day 43	Day 113 (Dosing Day)	Dosing Day 113	nue q12week dosing	12 Weeks: Weeks 28, 40, 52, 64, 76, 88, 100, 112, 124, 136, 148, 160, 172, 184, and 196	Dosing	See footnote 5 for timing	Dose	pletion ⁶	matton
Windows (in days)	-60 to -1	-30 to -1		+1	± 5	± 5	+1	± 5	± 14	+1		± 14	+1	± 14	± 5		
Informed Consent	X										unti						
Eligibility Criteria	X										until last						
Demographics/Medical History	X										patient						
PiZZ Genotype	X										t with						
Height, Weight, BMI	X										h fib						
Weight only			X			X			X		fibrosis	X				X	X
Urine Cotinine	x								Pre-dose X		s receives						
Urine Drug Screen	X										es 1						
Hepatitis/HIV	X										10 th d						
PFT (Spirometry and DLCO) ¹		X	Pre-dose X			Pre-dose X			Pre-dose X		dose (W	Pre-dose X				X	Х
FibroScan	X										(Week 100)			X			X
MRI (PDFF, Fe, MRE) ²	X										00)			X			X
Liver Biopsy ⁵	X													X			X
Vital Signs (BP, temperature, HR, RR)	x		Pre-dose & 1 hr post- dose X	x	х	Pre-dose & 1 hr post- dose X	х	х	Pre-dose & 1 hr post- dose X	x		Pre-dose & 1 hr post-dose X		х		х	х
Physical Exam ³	X		Pre-dose X	X	X	Pre-dose X	X	X	Pre-dose X	X		Pre-dose X				X	X

Table 2: Schedule of Assessments – Patients With Evidence of Fibrosis (Continued)

Assessment	Screen	1	Day 1 (Dosing	24 hrs After	Week 2	Week 4	24 hrs After	Week 6	Week 16	24 hrs After	Cont	Additional Dosing Visits	24 hrs After	Post-Dose Liver	90 Days Post	Study Com-	Early Term-
	Requir Prior to Day 1	to	Day)	Dosing Day 1	Day 15	Day 29 (Dosing Day)	Dosing Day 29	Day 43	Day 113 (Dosing Day)	Dosing Day 113	Continue q12week dosing	Every 12 weeks: Weeks 28, 40, 52, 64, 76, 88, 100, 112, 124, 136, 148, 160, 172, 184, and 196	Dosing	Biopsy ⁵ See footnote 5 for timing	Last Dose	pletion ⁶	ination ⁸
Windows (in days)	-60 to	-30 to -1		+1	± 5	± 5	+1	± 5	± 14	+1	dosing	± 14	+1	± 14	± 5		
ECG 7	X		Pre-dose X			Pre-dose X			Pre-dose X			Pre-dose X ⁷				X	x
Urine Pregnancy Test 9	X		Pre-dose X			Pre-dose X			Pre-dose X		Hast	Pre-dose X				X	х

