FSH (post-menopausal females)	X										patier						
Clinical Labs (heme, coag, trop, chem, lipids, urinalysis) ⁴	Х		Pre-dose X	Х	х	Pre-dose X	х	х	Pre-dose X	Х	until last patient with fibrosis	Pre-dose X		х		х	х
PRO-C3/PRO-C6	X								X		brosi	Pre-dose X		X		x	x
Calculate APRI			Pre-dose X						Pre-dose X		receives	Pre-dose X (Weeks 40, 64, 88, 112, 136, and 160)		х		х	х
Anti-drug Antibodies	X		Pre-dose X			Pre-dose X			Pre-dose X		10 th dose	Pre-dose X				X	х
Z-AAT Level	X		Pre-dose X		X	Pre-dose X		X	Pre-dose X		se (W	Pre-dose X		х		Х	х
Serum Alpha-1 Antitrypsin Level	X		Pre-dose X		X	Pre-dose X		X	Pre-dose X		(Week 100)	Pre-dose X		х		Х	Х
Concomitant Meds/Therapies	X		X	х	X	X	Х	X	X	X	ē	х		х		Х	x
Adverse Events	X		X	X	X	X	X	X	X	X		X		X		X	X
Study Treatment			X			X			X			X					
Pharmacokinetics (PK)			Pre-dose, 1 hr, & 2 hr post-dose X	X					Pre-dose, 1 hr, & 2 hr post-dose X	X							
Phone Call to Assess AEs													X				
Phone Call to Assess for Pregnancy Post-dose															Х		

- 1. Pulmonary function testing includes: Spirometry including VC, FVC, FEV₁, FEV₁/VC, FEV₁/FVC, and DLCO. Pertinent study FEV₁ will be based on post-bronchodilation value. Spirometry testing at Screening is to determine inclusion/exclusion. Spirometry and DLCO may be repeated once per timepoint. Spirometry and DLCO should also be conducted any time a patient experiences a COPD exacerbation. For dosing visits between Week 28 and Week 196, DLCO can occur once every 6 months.
- 2. MRI hepatoscan will include magnetic resonance elastography (MRE), hepatic fat content by MRI-PDFF (or equivalent) and hepatic iron content. MRI should always be completed before biopsy (if performed on the same day) and after a 4-hour fast from food.
- 3. A complete physical exam (PE) is to be performed at Screening and Study Completion/Early Termination. A symptom-directed PE is to be performed at all other designated visits. Genitourinary exam may be deferred.
- 4. Patients should be fasting (water only) for a minimum of 2 hours prior to collection of the clinical labs.
- 5. A post-dose biopsy visit will occur at Week 48 (± 2 weeks) for patients with evidence of fibrosis at Screening. For patients beyond Week 48 at the time of IRB/EC approval of Protocol v4.0, the post-dose liver biopsy will be performed at Week 72 (± 4 weeks) or Week 96 (± 4 weeks).
- 6. The Study Completion visit can occur 4 to 12 weeks from the last study dose.

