4.8. Risk Assessment for Patients

Based on the safety review of nonclinical and clinical trials, the following are considered as identified risks or potential risks:

Identified risks:

• Injection Site AE Risk: Adverse events (AEs) at the injection site (e.g., erythema, pain, etc.) have been reported with administration of fazirsiran in clinical studies AROAAT1001, AROAAT2001, and AROAAT2002 and are therefore considered an identified risk. All were deemed to be non-serious and resolved without sequelae. The majority of the injection site reactions (ISRs) were mild in severity. Other siRNA antisense oligonucleotides (ASOs) in clinical trials have been associated with usually mild ISRs. This study includes directions for assessing injection site AE intensity based on pre-defined criteria (see Section 10.5.2). Additionally, steps will be taken to minimize ISRs such as rotating injection sites and allowing the fazirsiran solution to come to room temperature prior to injecting.

Potential risks (monitored in this study using diagnostic evaluations, assessments, and study modification rules):

- Liver Biopsy Risk: Performance of liver biopsies is commonly part of the standard of care in patients with liver disease related to AATD as well as other adult liver diseases. While it is a common procedure, like any procedure it is associated with some risk. See Appendix 5 for more information about risks associated with study assessments such as liver biopsy.
- Pulmonary Risk: AATD may manifest as pulmonary disease in adult patients. AATD pulmonary disease is often treated with AAT augmentation therapy in countries where this therapy has been approved and is available. Fazirsiran is intended to reduce hepatic production of AAT and will, by extension, reduce serum levels of AAT protein. In AATD patients, this protein is poorly functional in its capacity to inhibit neutrophil elastase relative to wild type protein. Pulmonary disease in AATD requires decades to develop, especially in the absence of smoking, and it is extremely unlikely that short-term reduction in serum AAT will worsen pulmonary disease, particularly in non-smokers. The Sponsor anticipates an approximate 90% reduction of serum AAT to represent near maximum reduction possible with a hepatocyte targeted RNAi mechanism based on previous experience. Extra-hepatic production, including locally in the lung, is not expected to be reduced by fazirsiran.

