Based on the lack of a consistent pattern of adverse changes in pulmonary function metrics seen in the AROAAT1001 study using siRNA to transiently reduce serum AAT levels, and the fact that the native Z-AAT has reduced inhibitory effect against neutrophil elastase, the reduction of serum Z-AAT should not significantly impact any protective effect. Pulmonary disease in PiZZ patients with very low serum AATD takes decades to develop. PiZZ patients already have very low serum AAT levels and a further reduction in already low AAT may not influence pulmonary function. Additionally, many of these patients are on AAT augmentation therapy or may be given augmentation therapy and will continue it during the trial. Steps will be taken in this study to mitigate this theoretical risk.

1. Patients who smoke or with a significant smoking history will be excluded from this study and their non-smoking status will be confirmed by measuring urinary cotinine at Screening and with repeat confirmatory checks during the study. Patients with a positive

urine cotinine during the study (with positive result confirmed on repeat) will be counseled on the importance of not smoking during the study.

- 2. Patients with severe and unavoidable exposure to inhaled environmental exposure will be excluded.
- 3. Above standard of care pulmonary monitoring is implemented during the study with vital capacity (VC), forced vital capacity (FVC), forced expiratory volume in one second (FEV₁), ratio of the forced expiratory volume in the first one second to the forced vital capacity of the lungs (FEV₁/FVC), and the ratio of the forced expiratory volume in 1 second to vital capacity (FEV₁/VC), measured pre-dose and at every dosing visit. Diffusing capacity for carbon monoxide (DLCO) is measured every dosing visit through Week 16 and then every other dosing visit.
- 4. Patients without sufficient pulmonary reserve at baseline (e.g., post-bronchodilation FEV₁ <65 % of predicted) are excluded. Patients with recent lower respiratory infections (such as pneumonia) are also excluded.
- 5. Standard of care emphysema treatment (e.g., corticosteroids, bronchodilators) is permitted.

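### Table 2 schedules urine cotinine only at Screening and Week 16, so fibrosis patients do not get the continuing non-smoking checks that criterion 5 and Section 4.8 call for

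*Protocol*

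**What the plan says.** Two places in the protocol commit to cotinine testing after entry. Section 7.2, criterion 5, asks for "current non-smoking status confirmed by urine cotinine at Screening and throughout the study". Section 4.8, item 1 of the pulmonary mitigations, says that "non-smoking status will be confirmed by measuring urinary cotinine at Screening and with repeat confirmatory checks during the study". It then gives the consequence for anyone who tests positive: "urine cotinine during the study (with positive result confirmed on repeat) will be counseled on the importance of not smoking during the study". Section 9.3.6 also mentions testing at Screening and during the study, but gives no timepoints and refers to the Schedule of Assessments.

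The schedules are narrower. The "Urine Cotinine" row of Table 2 (patients with fibrosis) is marked at Screening and at Week 16 pre-dose, and no footnote adds a test. The same row of Table 1 (patients without fibrosis) is marked at Screening, Week 16 and Early Termination.

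Section 7.5, item 3, separately requires patients to abstain from smoking, e-cigarettes included, for as long as they are in the study.

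**The concern.** A site that follows Table 2 exactly performs one cotinine test after entry and then none, however long dosing continues. That does not meet criterion 5, and it does not amount to the repeat checks of Section 4.8.

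The gap matters because of what Section 4.8 rests on non-smoking. It judges it "extremely unlikely that short-term reduction in serum AAT will worsen pulmonary disease, particularly in non-smokers". After Week 16 exposure is no longer short, since dosing continues to between Week 100 and Week 196, and non-smoking is no longer verified by test. After the post-dose biopsy (Week 48, 72 or 96) every continuing fibrosis patient receives 200 mg with no concurrent placebo group. Section 6.2 gives long-term safety as the purpose of that phase, and Section 6.4.6 of the SAP addendum summarises change in lung function at its visits. Smoking is an obvious competing explanation for a fall in FEV1 or DLCO in an uncontrolled phase, and no scheduled data would speak to it. Tobacco use is otherwise asked about only in the medical history (Section 9.3.1), which Table 2 schedules at Screening.

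**Working it through.** **Schedule arithmetic, reproducing the plan's own figures first.** Inputs are from Section 6.4 and Table 2: doses on Day 1, Week 4 and Week 16, then every 12 weeks to Week 196; Screening up to 8 weeks; Study Completion 4 to 12 weeks after the last dose.

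- Doses: 3 + 15 (Weeks 28, 40, …, 196) = 18, as stated.
- Duration: 8 + 196 + 12 = 216 weeks, as stated.

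**Table 2 read by column.** The tables were machine-read, so the lung-function row serves as a check on alignment. Its marks fall where expected, including the 12-weekly, Study Completion and Early Termination columns, so a lost cotinine mark is unlikely.

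| Table 2 column | Cotinine | Lung function | Clinical labs, incl. urinalysis |
|---|---|---|---|
| Screening | yes | yes | yes |
| Week 16 | yes | yes | yes |
| Weeks 28 to 196 | none | yes | yes |
| Post-dose biopsy | none | none | yes |
| Study Completion | none | yes | yes |
| Early Termination | none | yes | yes |

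**Size of the gap, fibrosis patients.**

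- Last dose at Week 100: visits at Weeks 28, 40, 52, 64, 76, 88 and 100 = 7 without cotinine; 100 − 16 = 84 weeks, or 84/100 = 84% of dosing time.
- Last dose at Week 196: 15 visits without cotinine; 196 − 16 = 180 weeks, or 180/196 = 92%.
- To Study Completion after a Week 196 dose: 180 + 4 = 184 to 180 + 12 = 192 weeks.

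The gap is shorter for a patient who leaves early or whose site opens an extension study sooner. Section 6.1 describes the dose selection as done "After all enrolled patients completed the Week 16 visit", so under this protocol version no fibrosis patient has a scheduled cotinine test ahead.

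**Size of the gap, patients without fibrosis.** At most about 36 − 24 = 12 patients. Lung function is tested at Weeks 28, 40, 52 and 64 (4 visits) with no cotinine; 64 − 16 = 48 weeks, or 48/64 = 75% of follow-up. The Early Termination test applies only to those who leave early.

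**Effect of the proposed change.** Section 4.8, item 3, says DLCO "is measured every dosing visit through Week 16 and then every other dosing visit"; footnote 1 of Table 2 allows it once every six months. Cotinine at the same visits gives:

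- To Week 100: Weeks 40, 64, 88 (3) or Weeks 28, 52, 76, 100 (4), plus 1 at the end = 4 to 5 tests.
- To Week 196: Weeks 40, 64, …, 184 (7) or Weeks 28, 52, …, 196 (8), plus 1 at the end = 8 to 9 tests.
- Longest nominal gap: 2 × 12 = 24 weeks, against 84 to 180 dosing weeks now. If the last such visit is Week 88 or 184 and the last dose is 12 weeks later, the gap to Study Completion is 12 + 4 = 16 to 12 + 12 = 24 weeks.

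**The case against.** The strongest reply is that little protection is lost. The obligation to abstain (Section 7.5) continues, and non-compliance is a ground for withdrawal (Section 7.4). The lung safeguards do not depend on cotinine: spirometry at every dosing visit, weekly sponsor review with dosing suspended after a fall of more than 10% until a pulmonary consultation has taken place, DSMB review (Section 4.8, items 3, 7 and 8), and referral, augmentation therapy and more frequent spirometry under Appendix 3. The only stated consequence of a confirmed positive test is counselling. All of this stands. These safeguards, however, either state a rule without checking it or respond once lung function has fallen, and none names cotinine.

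A second reply is that the wording is loose. Only criterion 5 says throughout; Section 4.8 says repeat checks; neither sets a frequency; and a post-entry clause cannot work as an eligibility test. This is right, and a reader should not infer that Section 4.8 promises testing throughout. But its checks are plural, and one test does not meet that.

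A third reply is that six-monthly cotinine would not separate drug from smoking effects. Permitted patch or gum can make it positive, it samples each interval only once, and the open-label analysis is descriptive. This also stands: the data would annotate individual cases, not adjust an estimate.

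Three stronger inferences are not supported. The first is that smoking becomes permitted, or lung monitoring stops, after Week 16; neither happens. The second is that the dose-selection result is compromised; that analysis uses serum Z-AAT to Week 16 and does not draw on later cotinine. The third is that some number of smokers will be missed; the documents give no smoking rate, and entry is limited to patients without daily smoking for at least 12 months and with under 15 pack-years before that.

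**Conclusion.** The mismatch between text and schedule is real and worth correcting, at modest weight. For fibrosis patients, biochemical verification of non-smoking, and the counselling tied to it, have no scheduled trigger for 84 to 180 dosing weeks and 7 to 15 dosing visits. They also lack the Early Termination test that two-dose patients have, and the documents give no reason for the difference. The loss falls on the interpretation of long-term lung safety, chiefly in the uncontrolled open-label phase. The primary analysis, error control, power and eligibility are untouched.

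This rests on the column reading of Table 2 and on the absence of any other text that schedules cotinine. SAPv3.0, to which the addendum defers, was not available, so how it handles existing cotinine results is unknown.

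**What to change.** At the next protocol amendment:

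1. In Table 2, mark urine cotinine at the six-monthly DLCO dosing visits and at Study Completion and Early Termination. The "Clinical Labs (heme, coag, trop, chem, lipids, urinalysis" row already provides urine at each of these. In Table 1, mark it at Week 64 for any patient not yet there.
2. At the same visits, record smoking since the last visit. Nicotine-replacement use can be taken from the concomitant medications already collected (Section 9.3.9).
3. List cotinine-positive patients beside same-visit FEV1 and DLCO, unless SAPv3.0 already does so. The addendum plans no separate open-label listings, so this belongs in the overall listings.

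The cost is at most 4 to 5 assays per fibrosis patient to Week 100 or 8 to 9 to Week 196, fewer for visits already past; one per remaining patient without fibrosis; and a short eCRF item. The schedule change needs IRB/EC approval (Section 12.2). The benefit is prospective only: the 24-week maximum gap applies from adoption, and the documents do not say how many visits remain.

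If few remain, rewording criterion 5 and Section 4.8 to match the tables would also remove the mismatch, but by giving up part of a stated mitigation.
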